**Deep Learning Enabled Endovascular Stroke Therapy Screening
in Community Hospitals**

NCT05838456

Version Date: 02/09/2023

Protocol Title: Deep Learning Enabled Endovascular Stroke Therapy Screening in Community Hospitals

Protocol Version/Date: 3.0, 01/16/2023

Principal Investigator: [name], [name]

Co-Investigators: [name]

Key Study Personnel: [name]

Population: 5,000 subjects

Number of Sites: 4 Sites
Memorial Hermann Hospital – TMC
Memorial Hermann Hospital – Memorial City
Memorial Hermann Hospital – Southwest
Memorial Hermann Hospital – Woodlands

Study Duration: July 15th 2019 – March 01st, 2026

Subject Duration: Not applicable

Acute Ischemic Stroke (AIS) is the leading cause of long-term disability in the US, and every minute of delay from onset to treatment reduces the likelihood of good clinical outcome. As a result of our ongoing Comprehensive Stroke Center (CSC) quality improvement efforts, we have identified a key delay: time from the completion of computed tomography (CT) angiography of the head and neck to interpretation in the setting of AIS care. Motivated by this unmet need in clinical care, and in partnership with the UTHealth School of Biomedical Informatics, we recently developed a machine-learning algorithm to automate the interpretation of CT angiography (CTA) for the presence or absence of large vessel occlusion (LVO) and other stroke relevant information such as estimated stroke core size. We propose a prospective, cluster- randomized study to determine whether incorporating our automated machine learning (ML) algorithms to AIS care pathways reduces the time from patient ER arrival to imaging interpretation by sending automated alerts of its findings to physicians on the stroke care team. Physicians will ultimately decide if patients are eligible for thrombectomy, and all patients will receive the standard of care following current guidelines. This strategy is expected to help improve patient stratification procedures for endovascular thrombectomy by using commonly available data. Our unique research team consisting of machine-learning and AIS imaging experts will take advantage of the rich and diverse talents across the UTHealth Campuses and Memorial Hermann Hospital System.

Background Information

Acute Ischemic Stroke (AIS) is the leading cause of long-term disability in the US adult population with nearly 800,000 new patients affected by stroke annually in the US, and with Large Vessel Occlusion (LVO), a subtype of AIS that could require endovascular stroke therapy (EST), disproportionately contributing to stroke-related dependence and death.^{1,2} The last four years, however, have borne witness to rapid changes in care for patients with LVO AIS. In 2015, five randomized clinical trials established EST as one of the most significant advances in modern medicine.³⁻⁷ Compared to patients treated with medical management alone, LVO AIS patients treated with EST were nearly 2.5 fold more likely to achieve good neurological outcomes (number needed to treat = 3), a treatment effect size rivaling that of antibiotics to treat acute bacterial infections.^{8,9} Yet these advances have revealed shortcomings in our AIS systems of care, as we are now faced with a great number of patients that must be triaged with an increasingly complex evaluation that must be performed in a shorter time.

A known dogma is that time is brain in AIS. Every minute after an occlusion of the cerebral vasculature 2 million neurons die, and key quality metrics in AIS revolve around reducing the time from when the patient arrives to the hospital to when treatment is initiated.¹³ While we now know from the results of pivotal randomized clinical trials that EST, which re-opens occluded cerebral vessels through catheter-based procedures, can dramatically improve patient outcomes following AIS, these outcomes are still highly time-dependent.^{10,11} This challenge is particularly relevant in the non-Texas Medical Center MH campuses, where delays after imaging arise for two reasons. First, Neurologists caring for patients in these settings are not comfortable interpreting the imaging studies to determine the presence or absence of LVO without relying on a Radiologist interpretation, thereby adding an additional step to the care pathway. Second, for Neurologists evaluating these patients remotely through Telemedicine, the imaging studies may not be completed at the time of the initial evaluation, and the requirement for the physician to remember to check periodically to see when the imaging study is complete can lead to fall outs, particularly when they may have moved on to care for another patient.

Through our continuous process of quality improvement, we recently conducted an analysis of delays in AIS treatment. Among 833 patients with AIS, median time from ER arrival to CTA interpretation for presence or absence of LVO was 65 minutes [IQR 41 - 127]. In order to comply with our Joint Commission requirements for Comprehensive Stroke Center, the EST procedure must be initiated within 90 minutes from patient arrival to the ER, and given the multiple steps that must occur after the imaging result and before EST initiation, this time interval from ER arrival to imaging result was identified as a weak point in the process.

Motivated by this unmet need in clinical care, and in partnership with the UTHealth School of Biomedical Informatics, we recently developed a machine-learning algorithm to automate the interpretation of CTA for the presence or absence of LVO. This novel deep neural network architecture, named DeepSymNet, was trained on over 400 CTA studies, using the radiology report and expert readers interpretations as gold standard, and can nearly instantaneously analyze images for LVO.¹² We then validated this algorithm on a fully external dataset of 126 patients, and found that it can perform this task with very high discrimination (Figure 1).

Given these results, we propose a prospective, cluster-randomized study to determine whether AIS care pathways incorporating image based ML algorithms reduces the time from patient ER arrival to imaging interpretation (Figure 2). Our unique research team consisting of machine-learning and AIS imaging experts will take advantage of the rich and diverse talents across the UTHealth Campuses and the Memorial Hermann Hospital System. Given our preliminary findings, we hypothesize that integration of these approaches into the AIS care pathway will reduce delays from CTA acquisition to interpretation, without requiring any change in existing CT hardware or acquisition protocols.

Objectives

The expected outcome is the creation of a state-of-the-art infrastructure for deploying artificial intelligence algorithms in the clinical practice and a thorough evaluation of a potential paradigm shifting approach for a measurable and sustainable quality improvement of stroke care.

Study Design

To test the previously mentioned hypotheses, we propose a multi-center, stepped wedge cluster-randomized study that will include patients across 4 hospitals in the Memorial Hermann/UTHealth stroke system of care in the greater Houston area. The software will be randomly enabled at each of 4 comprehensive stroke center hospitals to evaluate the impact of this software on primary and secondary outcomes. The primary outcome will be the time from patient ER arrival to initiation of EST (“door-to-groin” time). Secondary outcomes include the number of patients treated with EST and 90-day disability outcomes.

Study Population

The alert system will be enabled for all CT angiography imaging studies for participating Hospitals. A valid sample will be one that satisfy the following criteria:

Inclusion Criteria

1. Male or Female, 18 years of age or older.
2. Patients who present to the emergency department with signs and/or symptoms concerning for acute ischemic stroke.
3. Patients who undergo CT angiography imaging
4. Patients determined to have a large vessel occlusion acute ischemic stroke. This determination will be made based on official radiology report for the CT angiography imaging.

Exclusion Criteria

1. Patients with incomplete data on the electronic medical record.

Study Procedures

ML Algorithms Integration

Custom ML software (Viz.AI) will be installed on a server and receive data from the centralized PACS system. This software has been purchased by the MH hospital system for commercial use. The system will then send alerts to the care team through notifications pushed through the Viz.AI app present on the physician, nurse and technologist's mobile phone. Diagnosis and treatment decisions will be based on the clinical evaluation and review of the images by the treating physician, as per routine standard of care. This study will not interfere with routine clinical work. Data capture will be performed after treatment decisions and care have been delivered.

Clinical Data Acquisition

Clinical data will be collected at each of the participating sites as a part of our ongoing Comprehensive Stroke System quality improvement protocols. All other clinical and outcome data will be collected through electronic medical record review. Captured data will include patient demographics, past medical history, imaging utilization and imaging findings, time intervals (i.e. time from last known well to presentation, time from door to imaging, time from door to IV tPA, time from door to groin puncture), procedural outcomes (i.e. TICI scores, hemorrhage rates), discharge clinical outcomes, and in patients who received EST or IV tPA, 90-day disability outcomes. These data are routinely captured per standard-of-care at our Comprehensive Stroke System and will be used for analysis as a part of this study.

Ethics

Being an observational project, there will be no interventions, investigations, tests, drugs, and/or interviews administered to patients. We do not expect any research-related adverse events. All personal health information from patients will be kept confidential and in compliance with HIPAA regulations. This site is seeking waiver of consent for this observational study involving electronic medical chart review and analysis of de-identified CTA images.

Risks and benefits for the human subjects

Risks

In this study, ML algorithms are not used for diagnosis, cure, mitigation, treatment or prevention as it only sends alerts. All diagnosis and treatment decisions are still based on the clinical evaluations and radiology reports. As such, we do not foresee that this study poses more than minimal risk encountered during the routine stroke care.

Benefits

We do not foresee any immediate benefits for the human subjects involved. However, if successful, this study could enable a faster time-to-treatment for stroke patients.

Data handling and record keeping

Imaging Data

The server running the ML algorithm will be hosted by Viz.AI. This server and imaging transfer protocol have been reviewed by MH IT and found to fall within acceptable security parameters. The Viz.AI software is a commercial product, and its usage in this study will fall within the boundaries of its intended use as a commercial product and the contract with MH hospital.

Clinical Data

All the clinical numerical variables collected for this study will be anonymized and stored in a central RedCap database inside the UTHealth network. All users of this database will comply with HIPAA regulations and with Good Clinical Practice for the handling of electronic clinical data. Only the study key personnel will have access to the project data.

Each subject will be given a unique subject identification which will be linked to the subject's MRN for prospective data collection. If data is to be analyzed, no patient identifier will be included to ensure no patient can be tracked or identified. Thus, analysis will solely be performed on de-identified data. No paper records will be kept. To ensure reproducibility of the finding, the UTHealth RedCap will continue to store the data after the completion of the study and until IT resources will allow to maintain the machine updated and protected. If this is not possible, all the data containing Protected Health Information (PHI) will be destroyed.

Data Sharing

In order to allow for a broader reach for our finding and scientific publications, we might have to share part of the data for scientific non-commercial purposes. In this case, we will strip the imaging and clinical data of any PHI information.

Publication Plan

Results based on data gathered from this study may serve to elaborate abstract submissions or manuscripts for peer-reviewed journals. Research publications will not include any patient-specific information or identifiers.

References

1. Benjamin, E.J. *et al.* Heart Disease and Stroke Statistics-2018 Update: A Report From the American Heart Association. *Circulation* **137**, e67–e492 (2018).
3. Berkhemer, O. A. *et al.* A randomized trial of intraarterial treatment for acute ischemic stroke. *N. Engl. J. Med.* **372**, 11–20 (2015).
4. Campbell, B. C. V. *et al.* Endovascular therapy for ischemic stroke with perfusion-imaging selection. *N. Engl. J. Med.* **372**, 1009–1018 (2015).
5. Goyal, M. *et al.* Randomized assessment of rapid endovascular treatment of ischemic stroke. *N. Engl. J. Med.* **372**, 1019–1030 (2015).
6. Saver, J. L. *et al.* Stent-retriever thrombectomy after intravenous t-PA vs. t-PA alone in stroke. *N. Engl. J. Med.* **372**, 2285–2295 (2015).

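### Does it matter that the stated aim speaks of the team's own algorithm when the software switched on is Viz.AI?

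*Protocol*

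**What the plan says.** The opening summary says that the team, working with a university informatics school, recently built an algorithm to read CT angiography. The sentence that sets the aim then proposes to "determine whether incorporating our automated machine learning (ML) algorithms to AIS care pathways reduces the time".

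Background Information gives the algorithm its name, "This novel deep neural network architecture, named DeepSymNet", and reports its validation in 126 patients. The paragraph that follows proposes the trial. It restates the aim for image-based machine learning in general, without a product name, and ends with the hypothesis: "Given our preliminary findings, we hypothesize that integration of these approaches into the AIS care pathway will reduce delays".

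Study Design randomises when the software is enabled at each of 4 hospitals. Study Procedures, under ML Algorithms Integration, identifies that software: "Custom ML software (Viz.AI) will be installed on a server and receive data from the centralized PACS system". It adds: "This software has been purchased by the MH hospital system for commercial use". Alerts go out through the Viz.AI app.

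Data handling and record keeping, under Imaging Data, agrees: "The server running the ML algorithm will be hosted by Viz.AI", and "The Viz.AI software is a commercial product, and its usage in this study will fall within the boundaries of its intended use".

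**The concern.** On a straight reading, the trial appears to promise a test of one algorithm and deliver a test of another. The possessive in the summary's aim comes directly after the account of the team's own development work, so a reader will take it to mean that work. The only detection performance reported in the protocol belongs to DeepSymNet, and the hypothesis appeals to the team's preliminary findings. The tool that is switched on is a purchased commercial product, yet the procedures call it custom. The visible text never says that one runs inside the other, replaces it or is equivalent to it.

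What would be at stake is attribution. Comparing periods with and without the alerts measures the effect of the alerts actually sent. If those come from Viz.AI, neither a positive nor a null result says anything about DeepSymNet. A publication framed on the summary's aim could credit, or blame, software that was enabled at no hospital.

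**Working it through.** No formula applies and the plan gives no figure to reproduce on this point. The check sets the relevant places side by side and asks whether anyone following the protocol could go wrong.

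**Step 1. Which software is named where**

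| Place in the protocol | Function of the text | Software |
|---|---|---|
| Opening summary | Aim | The team's own, unnamed |
| Background Information | Rationale | DeepSymNet (1 mention) |
| Background Information, proposal paragraph | Aim restated, hypothesis | Image-based algorithms in general |
| Objectives | Expected outcome | Artificial intelligence algorithms in general |
| Study Design | What is randomised | The software, unnamed |
| ML Algorithms Integration | What is installed and sends alerts | Viz.AI (2 mentions) |
| Imaging Data | Hosting and commercial status | Viz.AI (2 mentions) |
| Figure 1 title and caption | Preliminary performance | DeepSymNet (2 mentions) |

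Totals: Viz.AI 2 + 2 = 4; DeepSymNet 1 + 2 = 3. No section names both. The split follows function: text that tells people what to do names Viz.AI, and text that explains why the idea is promising names DeepSymNet.

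**Step 2. Could a site enable the wrong system?** No. The installation, purchase, alert channel and server host are all given, and all point to the same commercial product. Nothing instructs anyone to install DeepSymNet.

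**Step 3. What does the comparison estimate?** The effect of having Viz.AI alerts enabled against not having them. That is fixed by what is switched on, whatever possessive the summary uses.

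**Step 4. Does the hypothesis depend on DeepSymNet?** Not clearly. Background Information reports two sets of the team's own findings: the delay analysis in 833 patients (median 65 minutes, IQR 41 to 127) and the validation in 126 patients. The hypothesis is about shortening delays, so the preliminary findings it cites can include the first set. The approaches it mentions most naturally refer to the product-neutral restatement of the aim in the same paragraph, and that wording covers Viz.AI. Even if only the validation were meant, showing that one algorithm can detect large vessel occlusion is an ordinary reason to test alerting tools of that class.

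**Step 5. Is the custom label a contradiction?** It is ambiguous. It may mean an installation configured for the hospital system, which is compatible with a bought product. The later statements on purchase and commercial use leave no doubt about which product it is.

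**Step 6. What would corrected wording change?** Put Viz.AI alerts into the aim and drop the adjective. The randomisation, eligibility criteria, outcomes, data capture and target of 5,000 subjects all stay exactly the same.

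**The case for a change.** The strongest opposing case is that the summary sentence is the study aim and cannot be dismissed as motivation. Study Design opens by saying that it tests the hypotheses already given, so the design is formally tied to that text. A product-neutral restatement later on does not cancel a specific claim made first. Identifying the intervention is the protocol's job, so a separate analysis plan would not excuse the conflict. Someone who reads only the summary, an ethics reviewer for instance, could not tell whether an in-house algorithm or a marketed product is being deployed. The repair would cost a few words.

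Part of this stands. The possessive is wrong for what is deployed, the visible text gives no performance data for Viz.AI, and results from this trial cannot validate or refute DeepSymNet. The predicted harm does not follow, however. Nothing in the visible text plans to credit the result to DeepSymNet: the Objectives speak of artificial intelligence algorithms in general, and the Publication Plan attributes nothing to any product. A report has to describe its intervention, and an author who turns to Study Procedures finds Viz.AI. That a repair is cheap does not make it a defect in the plan.

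**Conclusion.** This is a clerical slip in descriptive text, and no change to the plan is needed. Its extent is one possessive in the opening summary and one unclear adjective under ML Algorithms Integration. The reading that ties the hypothesis to DeepSymNet alone is not forced by the text. The effect on the comparison, the outcomes and the numbers is nil. Following the operative sections as written, the sponsor would enable, analyse and report Viz.AI alerts.

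The conclusion rests on two assumptions. First, the operative sections describe what is really deployed, so DeepSymNet does not run behind the Viz.AI app. Second, the report names the intervention as the procedures do and claims nothing for DeepSymNet. Figure 2, which outlines the proposed approach, could not be seen, so the finding that nothing links the two systems applies to the visible text only. If either assumption failed, the matter would become one of substance.

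### 90-day disability is an unrestricted secondary outcome in LVO patients, but its capture is provided for only in those given EST or IV tPA, a subset fixed after allocation

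*Protocol*

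**What the plan says.** Study Design describes a stepped wedge trial in four hospitals, with the software switched on at random "to evaluate the impact of this software on primary and secondary outcomes". The same paragraph then states: "Secondary outcomes include the number of patients treated with EST and 90-day disability outcomes". No treatment restriction is attached to the disability outcome.

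The inclusion criteria define the sample by age, presentation, CT angiography and the radiology report: "Patients determined to have a large vessel occlusion acute ischemic stroke". Receiving EST or IV tPA is not a criterion.

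Clinical Data Acquisition lists what is recorded. Its closing items are "discharge clinical outcomes, and in patients who received EST or IV tPA, 90-day disability outcomes". The treatment condition attaches to the 90-day item; the discharge item beside it has none. The section adds that these are routinely collected data and will be used for the analysis. Nowhere does the protocol provide for a 90-day value in LVO patients who received neither treatment.

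**The concern.** A hospital's software status is set before a patient arrives. Whether that patient gets EST is decided afterwards, once the alert (if any) has gone out, and the number treated with EST is one of the effects the trial intends to measure. Comparing 90-day disability between software-on and software-off periods among treated patients therefore conditions on something the software may change.

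The protocol gives some reason to think it might. The opening summary says: "This strategy is expected to help improve patient stratification procedures for endovascular thrombectomy by using commonly available data". Background Information says that "the requirement for the physician to remember to check periodically to see when the imaging study is complete can lead to fall outs". If patients who would have gone untreated now receive EST, they have a 90-day value in on periods, while similar patients in off periods have none scheduled. Two things follow. The gain to the newly treated, which may be the software's main clinical benefit, is not measured. The comparison also mixes any real effect with a change in who is counted.

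A smaller point is linked to this. The only exclusion criterion is "Patients with incomplete data on the electronic medical record". Read strictly, it could remove untreated LVO patients because they lack a 90-day score, which would carry the selection over to the other outcomes.

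**Working it through.** The protocol states no figure to reproduce: it gives a population of 5,000 but no treated share, outcome rate or expected effect. The check is a comparison of the text, followed by an illustration on assumed values.

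**Text side by side**

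| Item | Section | Population |
|---|---|---|
| Sample | Inclusion Criteria | All adults with radiology-confirmed LVO |
| 90-day disability as an outcome | Study Design | No restriction stated |
| 90-day disability as captured | Clinical Data Acquisition | EST or IV tPA recipients |
| Discharge outcome as captured | Clinical Data Acquisition | No restriction stated |

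**Notation (all values assumed)**

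- *T*: share of LVO patients given EST or IV tPA in off periods; 50%, 70% or 85%.
- *x*: share of the cohort moved from neither treatment to EST in on periods; 0 to 10 points.
- *a0*, *a1*: good-outcome rate of the already treated, off and on.
- *m0*, *m1*: good-outcome rate of the movers, off (untreated) and on (treated).
- *d* = *m1* − *a1*.

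Moves from IV tPA alone to IV tPA plus EST stay inside the captured set and do not enter *x*.

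**Formulas**

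- Captured-set difference = (T·a1 + x·m1)/(T + x) − a0 = (a1 − a0) + d·x/(T + x).
- Share of the on-period captured set with no captured off-period counterpart = x/(T + x).
- All-LVO difference = T·(a1 − a0) + x·(m1 − m0), if those treated in neither condition are unaffected.

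The term *m0* appears in the all-LVO difference but not in the captured-set difference. That is the unmeasured benefit. The term d·x/(T + x) is the distortion.

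**Results**

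| x | Quantity | T = 50% | T = 70% | T = 85% |
|---|---|---|---|---|
| 0 | No counterpart | 0% | 0% | 0% |
| 3 points | No counterpart | 0.03/0.53 = 5.7% | 0.03/0.73 = 4.1% | 0.03/0.88 = 3.4% |
| 3 points | Shift, d = 10 points | 0.57 | 0.41 | 0.34 |
| 3 points | Shift, d = 20 points | 1.13 | 0.82 | 0.68 |
| 10 points | No counterpart | 0.10/0.60 = 16.7% | 0.10/0.80 = 12.5% | 0.10/0.95 = 10.5% |
| 10 points | Shift, d = 10 points | 1.67 | 1.25 | 1.05 |
| 10 points | Shift, d = 20 points | 3.33 | 2.50 | 2.11 |

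Shifts are in percentage points and take the sign of *d*.

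**Can the sign reverse?** Assume T = 50–70%, x = 5–15 points, a0 = a1 = 45%, m0 = 15% and m1 = 30%.

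- All-LVO difference = 15·x: from 15 × 0.05 = +0.75 to 15 × 0.15 = +2.25 points.
- Captured-set difference = (30 − 45)·x/(T + x): from −15 × 0.05/0.75 = −1.0 to −15 × 0.15/0.65 = −3.5 points.

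On these assumptions the software helps LVO patients, yet the treated-only comparison shows harm.

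**The case against.** The strongest reply is that Study Design gives no analysis population for any outcome, so the capture list may simply be the operational detail. Door-to-groin time is also listed without restriction, although it exists only in EST patients, and a statistical analysis plan that is not shown could define the population. This does not remove the problem. Door-to-groin time is undefined without EST, whereas 90-day disability exists for every LVO patient. An analysis plan could restrict or relabel the comparison, and indeed much of the remedy below is relabelling, but it could not supply scores that the protocol does not schedule.

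It is also fair that the capture list is not worded as exhaustive. Still, a condition placed on the 90-day item would serve no purpose if capture were universal, so restricted capture is the natural reading.

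Three points stand in part:

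- Evidence that treatment receipt will change is thin. The remark on fall-outs concerns the campuses outside the Texas Medical Center and may mean delay rather than missed treatment. Better stratification could also move patients out of EST, which the table does not model; the off-period set would then hold patients without on-period counterparts.
- The size is wholly assumed and may be modest against sampling error. Take 5,000 analysable patients split evenly, a 50% outcome rate, no clustering and x = 10 points. The standard error is √(0.25/1250 + 0.25/1500) = 1.9 points at T = 50% and √(0.25/2125 + 0.25/2375) = 1.5 points at T = 85%. Shifts of 1.1–1.7 points are below one standard error; shifts of 2.1–3.3 points are about 1.4–1.7. Unlike sampling error, though, the bias does not shrink with more patients.
- Treated-only capture may be a constraint of a chart-review study under a consent waiver. That is a reason to word the outcome accordingly, not to leave it unrestricted.

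**Conclusion.** The concern holds. As written, the protocol promises the software's effect on 90-day disability in LVO patients and provides data for a subset chosen after allocation by a decision the software may influence. The mismatch in the text is certain; the size of any bias is not. It is zero if nobody moves into or out of the captured set. It is also zero if newly and already treated patients do equally well, although the benefit to the newly treated then still goes unmeasured. On the assumed ranges above, moves of 3 to 10 points with outcome differences of 10 to 20 points shift the comparison by 0.3 to 3.3 points in either direction.

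This concerns a secondary outcome, so it should be corrected but does not affect the primary comparison. The point about the incomplete-record exclusion is a clarification, and the conclusion does not depend on it.

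**What to change.** 1. In Study Design, make the clinical-outcome comparison in all LVO patients on the discharge outcome, which Clinical Data Acquisition records without a treatment limit, and name the measure.
2. In the same place, restate 90-day disability as assessed in patients given EST or IV tPA, descriptive, and not evidence of the software's effect in the LVO cohort. Report beside it the share of LVO patients given EST or IV tPA in on and off periods, so the reader can see whether the captured set changed.
3. Under Exclusion Criteria, add a clause that a 90-day value not scheduled for capture does not count as incomplete data.

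The cost is revised outcome wording and one clause; no new data collection is needed. The drawback is that discharge status is earlier and coarser than 90-day disability, and the protocol does not yet define it. If the sponsor wants a 90-day effect for the whole LVO cohort, the score would have to be captured in untreated patients too, in both conditions. That is a larger change, and it would have to be squared with the Ethics section, which describes chart review without interviews under a waiver of consent.
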